10.4 Event Free Survival

The event free survival (EFS) is defined as the period from the first day of administration of study drug until the first occurrence of relapse, progressive disease, secondary cancer, or death or, if none of these events occurred, until the last contact with the subject.

Progression is defined as the appearance of any new lesions >10mm on CT/MRI, any new lesions on MIBG or new disease present in the bone marrow.

10.5 Overall Survival

Overall Survival (OS) will be defined as the first day of administration of study drug until death or will be censored at the last contact with the subject if death did not occur during the study. Overall survival will be monitored on an ongoing basis during the study, then every 6 months from the time the subject is off-study treatment up to a period of 2 years, then yearly for up to five years total.

11.0 ADMINISTRATIVE PROCEDURES

11.1 Patient Informed Consent

No study related procedures will be performed until a patient or a patient's legal representative has given written informed consent. The lead site will provide to the site Investigators a sample informed consent document that conforms to all the requirements for informed consent according to ICH GCP and US FDA guidelines (21 CFR 50). However, it is up to each site Investigator to provide a final informed consent that may include additional elements required by the Investigator's institution or local regulatory authorities. The IRB/EC for each investigational site must approve the consent form document prior to study activation; changes to the consent form during the course of the study may also require IRB/EC approval. The informed consent document must clearly describe the potential risks and benefits of the trial, and each prospective participant must be given adequate time to discuss the trial with the Investigator or site staff and to decide whether or not to participate. Each patient who agrees to participate in the trial and

who signs the informed consent will be given a copy of the signed dated and witnessed document. The original copy of the signed, dated, and witnessed informed consent document will be retained by the Investigator in the study files.

The Investigator must also obtain authorization from the patient to use and/or disclose protected health information in compliance with the Health Insurance Portability and Accountability Act (HIPAA). Written HIPAA authorization may be obtained as part of the informed consent process.

11.2 Ethical Conduct of the Study and IRB/IEC Approval

The study will be conducted according to the principles of the 2004 version of the Declaration of Helsinki, the International Conference on Harmonization Guidance on Good Clinical Practice and the requirements of all local regulatory authorities regarding the conduct of clinical trials and the protection of human subjects.

The Investigator will submit the protocol, the Investigator's Brochure, the informed consent and any other material used to inform patients about the trial to the local IRB/IEC for approval prior to enrolling any patient into the trial. The IRB/IEC should be duly constituted according to applicable regulatory requirements. Approval must be in the form of a letter signed by the Chairperson of the IRB/IEC or the Chairperson's designee, must be on IRB/IEC stationary and must include the protocol by name and/or designated number. If an Investigator is a member of the IRB/IEC, the approval letter must stipulate that the Investigator did not participate in the final vote, although the Investigator may participate in the discussion of the trial. The Investigator will also inform the IRB/IEC of any serious adverse events that are reported to regulatory authorities and will provide to the IRB/IEC a final summary of the results of the trial at the conclusion of the trial.

Any amendments to the protocol will be done at the lead site, and will be submitted to the IRB/IEC for review and written approval before implementation. These approved changes will then be forwarded to sites for review by their local IRB/IEC. Written approval from sites will be forwarded to the lead site.

11.3 Data Safety Monitoring Board (DSMB)

An independent Data Safety and Monitoring Board (DSMB) will oversee the conduct of the study. The members of this Board will receive database summaries, including adverse event reports, and will convene either in person or via teleconference every 6 months. The Board will be responsible for decisions regarding possible termination and/or early reporting of the study.

11.4 Monitoring and Auditing

A clinical monitor will make regularly scheduled trips to the investigational site to review the progress of the trial as defined in the Monitoring Plan. The actual frequency of monitoring trips will depend on the enrollment rate and performance at each site. At each visit, the monitor will review various aspects of the trial including, but not limited to, screening and enrollment logs; compliance with the protocol and with the principles of Good Clinical Practice; completion of

case report forms; source data verification; study drug accountability and storage; facilities and staff data quality; regulatory documentation; and study integrity. In addition the site may be audited by [REDACTED] government inspectors who must be allowed access to CRFs, source documents and other study files. The site must promptly notify the study chair of any inspections scheduled by regulatory authorities, and also forward copies of the inspection reports to the study chair. The study chair will promptly forward this information to [REDACTED].

During scheduled monitoring visits, the Investigator and the investigational site staff must be available to meet with the study monitor in order to discuss the progress of the trial, make necessary corrections to case report form entries, respond to data clarification requests and respond to any other trial-related inquiries of the monitor.

11.5 Pre-Study Documentation

Prior to initiating the trial, the Investigators at each site will provide to the Lead site the following documents:

- A signed FDA Form 1572
- A current curriculum vitae for the Principal Investigator and each sub-investigator listed on the FDA Form 1572
- A copy of the Investigator's medical license from the state in which the study is being conducted
- A letter from the IRB or EC stipulating approval of the protocol, the informed consent document and any other material provided to potential trial participants with information about the trial (e.g., advertisements)
- A copy of the IRB- or EC-approved informed consent document
- Current IRB membership list for IRB's without a multiple project assurance number or an IRB organization number under the Federal Wide Assurance program (www.ohrp.osophs.dhhs.gov).
- A signed Investigator Protocol Agreement
- A completed financial disclosure form for each person listed in box 6 of the FDA form 1572.
- Current laboratory certification for the reference laboratory
- A list of current laboratory normal values for the reference laboratory

11.6 Confidentiality

It is the responsibility of the investigator to insure that the confidentiality of all subjects participating in the trial and all of their medical information is maintained. Case report forms and other documents submitted must never contain the name of a trial participant. Each subject in the trial will be identified by a unique identifier that will be used on all CRF's and any other material submitted to the lead site. All case report forms and any identifying information must be kept in a secure location with access limited to the study staff directly participating in the trial.

The results of the study may be presented in reports, published in scientific journals or presented at medical meetings; however, subject names will never be used in any reports about the study.

11.7 Source Documents

The Investigator will maintain source records separate from the case report forms in the form of clinical charts, medical records, original laboratory, radiology and pathology reports, pharmacy records, etc. The Investigator will document in the clinic chart or medical record the name and number of the trial and the date on which the subject signed informed consent prior to the subject's participation in the trial. Source documents must completely reflect the nature and extent of the patient's medical care, and must be available for source document verification against entries in the case report forms when the monitor visits the investigational site. All information obtained from source documents will be kept in strict confidentiality.

11.8 Record Retention

The Investigator will retain the records of the study for 15 years, or for 2 years following the date that a marketing application for the study drug is approved, or if no marketing application is filed, or if such an application is not approved, for 2 years after the IND has been closed. The lead site will notify Investigators when retention of study records is no longer required. All study records must be maintained in a safe and secure location that allows for timely retrieval, if needed.

Study records that must be retained include copies of case report forms, signed informed consents, correspondence with the IRB or IEC, study drug dispensing and inventory records, source documents, clinic charts, medical records, laboratory results, radiographic reports) and screening/enrollment logs.

Should the Investigator relocate or retire, or should there be any changes in the archival arrangements for the study records, the lead site must be notified. The responsibility for maintaining the study records may be transferred to another suitable individual, but the lead site must be notified of the identity of the individual assuming responsibility for maintaining the study records and the location of their storage.

[figure not shown]
12.0 Biological Evaluation

A major challenge in the development of cancer therapeutics is an absence of understanding the relationship of the disease to response to therapy, and the ability to predict which subjects are most likely to respond to any particular agent. Emerging technologies including ability to establish primary tumor cells in culture, evaluate pharmacogenomics and explore biomarkers may provide a way to explore relationships between clinical benefit and treatment.

Urine Sample Analysis –

[REDACTED]

[REDACTED]

Blood and Bone Marrow Samples Analysis

ODC SNP analysis –Performed by Pediatric Oncology Translational Research Laboratory (Section 12.1.2)

Biomarker Analysis –Performed by Pediatric Oncology Translational Research Laboratory (Section 12.1.2)

Subject biomarkers will be evaluated in blood plasma using antibody array analysis in the laboratory of [name]. Antibody arrays will be generated to target biomarker candidates derived from gene expression, proteomic, and glycomic studies of tumor tissue (obtained from related biological studies). We will use these arrays to quantify the various protein levels in order to identify proteins or panels of proteins that differentiate patients with poor prognosis from patients with good prognosis. Specific carbohydrate levels also will be characterized on each protein to determine the associations of those measurements with prognosis.

Circulating Tumor Cell Analysis –Performed by [name] (Section 12.1.2)

[REDACTED]

Bone Marrow –Performed by [name] (Sections 12.1.3)

[REDACTED]

12.1 Pharmacokinetic Sample Instructions

Blood samples for the pharmacokinetic assay of DFMO and metabolites will be collected from approximately 10 currently enrolled subjects on their last day of taking the old DFMO formulation and on one day during Days 2-5 of taking the new formulation. Samples will be collected prior to administration of DFMO (Time 0) and at the following times: 30min, 1 hour, 3 hours, and 6 hours post-dose (exact time should be noted on CRF).

The blood samples will be processed to plasma, aliquoted and stored frozen at -80°C until assayed.

PK parameters (C_{max} , T_{max} , AUC_{0-24} , $AUC_{0-\infty}$, $t_{1/2}$, Cl , and Vd) will be determined as appropriate using standard noncompartmental procedures (WINNONLIN software). Individual subject measurements, as well as summary statistics (e.g., mean, standard deviation, range, %CV) will be reported.

Procedures for obtaining, storing and shipping of the pharmacokinetic samples are as follows:

1. One 2cc whole blood specimen will be collected in a purple top tube (EDTA) for each time point.
2. Place samples immediately in ice water bath until ready to process (no longer than 24 hours).
3. Specimen will be spun in a centrifuge at 2,000g for 15 minutes
4. Following centrifugation; using a clean pipette, the plasma from EDTA tube will be aliquoted into a plastic screw capped cryovial.
5. Specimens must be labeled with the participants unique study identifier, PK specific time point (include cycle, day, and time point) and date and time of specimen collection
6. Specimens will then be stored in a -80 freezer until ready to be shipped.

PK Specimen shipping:

- All specimens will be shipped on dry ice following the federal IATA hazardous Specimen Shipping Guidelines
- Specimens should be batch shipped (after each subject completes all PK time points) on a Monday-Thursday.
- PK Specimens will be shipped to the following address:

[name]

Pediatric Oncology Translational Research Laboratory

Coopers Landing

[name]

[name]

Ph: [contact]

[contact]

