3.0 Study Objectives

3.1 Primary Objective:

3.1.1 To evaluate the preventative activity of DFMO as a single agent in patients that are in remission based on: Event free survival (EFS)

3.2 Secondary Objectives:

3.2.1 Correlation of urinary polyamine levels with progression of disease in neuroblastoma.

3.2.2 To evaluate the preventative activity of DFMO as a single agent in patients with neuroblastoma who are in remission based on:

- Overall Survival (OS)

3.2.3 To continue to determine the safety and tolerability of DFMO as a single agent and in pediatric and young adult patients with high risk neuroblastoma that is in remission.

3.2.4 To evaluate the pharmacokinetics (PK) of new DFMO formulation in a minimum of 10 patients.

3.2.5 Biological Correlates to minimally include: 1) Urine: polyamine levels and blood inflammatory markers, 2) Blood- microRNA analysis as predictor of DFMO effect; ODC SNP analysis in DNA isolated from nucleated cells; circulating tumor cell analysis, and explorative biomarker analysis 3) Bone Marrow- flow cytometry of minimal residual disease of tumor; explorative biomarker analysis

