6.0 STUDY DRUG ADMINISTRATION

6.1 DFMO

6.1.1 Description, Formulation, and Storage of DFMO

The dosage form to be used in this study are provided as a convex tablet containing 250 mg of eflornithine HCl, monohydrate. The tablets are packaged and sealed in opaque white HDPE bottles, and each bottle contains 100 tablets.

The tablets are to be stored at room temperature (20-25⁰C).

6.1.2 DFMO Dosing Table Per Weight Group:

The following table will be used to determine dispensing of DFMO.

DFMO Dose:

BSA (m ²)	Tablets to be Dispensed for each dose	Total Tablets Per Day	Actual Mg/m ²
>1.5	Four (4) tablets orally twice a day	Eight (8)	625 and down per dose
0.75 to 1.5	Three (3) tablets orally twice a day	Six (6)	500 to 1000 per dose
0.5 to < 0.75	Two (2) tablets orally twice a day	Four (4)	675 to 1000 per dose
0.25 to < 0.5	One (1) tablet orally twice a day	Two (2)	500 to 1000 per dose
<0.25	Not eligible for trial		

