3. Bone marrow biopsy and aspirate is to be performed if the treating physician has concerns for progression (If bone marrow testing is being performed and the subject has signed informed consent for the use of tissue in the correlative biologic study as a post-treatment sample please send additional samples per section 12.0)

For patients in first remission who require evaluations for previous front line treatments that are different than the timing of the above schedule, contact the study chair for approval to accept the subjects previously scheduled evaluations instead of repeating the above studies.

End of Cycles 6, 12, and 27

Windows- The following should be done within +/-14 days of the start of the next cycle. For off-therapy/end of cycle 27 it should be done within 30 days (+7) after stopping study drug.

1. Audiogram

(Audiogram should also be done at any time point for any suspected hearing loss)

7.6 PK's for Currently Enrolled Subjects switching to new Formulation DFMO (approximately 10 subjects):

1. **Last Day of Old DFMO Formulation:** Blood for Pharmacokinetic sampling will be done on last day of taking old formulation*. Subject should be instructed to hold their morning dose of old DFMO. Pre-dose PK sample will be collected, and then subject will take old DFMO in clinic. In total, Samples will be collected pre-dose, (Time 0), as well as at 30min, 1 hour, 3 hours, and 6 hours post-dose (exact time should be noted on CRF). Plasma will be separated and frozen at -80°C until analysis per section 12.1.

* Change from old formulation to new formulation may take place on any day of any cycle after subject consents to new formulation and does not need to be on day 1 of a cycle.

2. Start new Formulation of DFMO- Subject should start new formulation at second dose of this day in clinic once all PK's are drawn, this will be Day 1 of new drug formulation.
3. **One day during Days 2-5 of taking on new formulation.** Blood for Pharmacokinetic sampling on one day during days 2-5 of taking the new formulation. Subject should be instructed to hold their morning dose of new DFMO. Pre-dose PK sample will be collected, and then subject will take new DFMO in clinic. In total, Samples will be collected pre-dose, (Time 0), as well as at 30min, 1 hour, 3 hours, and 6 hours post-dose (exact time should be noted on CRF). Plasma will be separated and frozen at -80°C until analysis per section 12.1.

7.7 Other Schedules:

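### AUC0-24 and AUC0-infinity are planned from samples ending 6 hours after one of two daily doses; read literally both misstate exposure, and a steady-state dosing-interval AUC would not

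*Combined protocol and SAP*

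**What the plan says.** The objective (section 3.2.4) is: "To evaluate the pharmacokinetics (PK) of new DFMO formulation in a minimum of 10 patients". The dosing table in section 6.1.2 is twice daily in every row, for example "Three (3) tablets orally twice a day".

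Section 7.6 sets out two PK days. On the last day of the old formulation, "Subject should be instructed to hold their morning dose of old DFMO"; a pre-dose sample is drawn, the dose is taken in clinic, and sampling follows. Then: "Subject should start new formulation at second dose of this day in clinic once all PK's are drawn". The second PK day is "on one day during Days 2-5 of taking the new formulation" (section 12.1). On both days the post-dose samples are at "30min, 1 hour, 3 hours, and 6 hours post-dose (exact time should be noted on CRF".

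The synopsis lists Cmax, AUC over 0-24 h, half-life, clearance and Vd as parameters to be determined, without qualification. Section 12.1 adds Tmax and AUC0-infinity and says that the parameters "will be determined as appropriate using standard noncompartmental procedures (WINNONLIN software". No section says how hours 6 to 24 are filled in, how the second daily dose is handled, whether steady state is assumed, or how much extrapolation is acceptable.

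**The concern.** A noncompartmental run on one sampled dose carries that dose's terminal slope forward. To reach 24 h it must bridge 18 unsampled hours, during which a second dose is taken that the calculation does not know about. The slope rests on two or three points. AUC0-infinity is a single-dose quantity. Computed from a profile in patients on repeated dosing, it also counts drug left over from earlier doses.

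On the old-formulation day the second dose is the new product, so no 24-hour old-formulation exposure is measured that day.

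The purpose is to characterise the new formulation next to the old. An error common to both days would cancel in the new/old ratio. An error that depends on absorption rate would not, and absorption may change when the formulation changes.

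**Working it through.** **No figure to reproduce.** The documents state no AUC, half-life, clearance or absorption rate. The check therefore uses an assumed model.

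**Inputs from the documents:** sampling at 0, 0.5, 1, 3 and 6 h; two doses a day; new formulation as the second dose on the old-formulation day, after the last sample.

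**Assumed:** 12-hour dosing interval, one-compartment oral model, F·D/V = 1, ka = 1.2/h, half-life 2.5-7 h, steady state.

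**Formulas**
- ke = ln 2 / half-life
- C(t) = sum over doses at d = 0, -12, -24, ... of ka/(ka - ke) × [exp(-ke(t - d)) - exp(-ka(t - d))]
- True interval AUC = 1/ke; true 24-hour AUC = 2/ke
- Estimate: linear trapezoid over 0-6 h, with slope λ = ln(C3/C6)/3 carried forward from 6 h

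**Worked case, half-life 3.5 h.** Concentrations are 0.1226, 0.5385, 0.7223, 0.6961 and 0.4015.
- AUC0-6 = 0.165 + 0.315 + 1.418 + 1.646 = 3.545
- λ = 0.1835, so C6/λ = 2.188
- Literal AUC0-24 = 3.545 + 2.188 × (1 - exp(-18λ)) = 5.653, against a true 2/ke = 10.099: 56%
- AUC0-infinity = 3.545 + 2.188 = 5.73, against an interval AUC of 5.049: 1.14 times, with 2.188/5.73 = 38% extrapolated
- AUC0-12 = 3.545 + 2.188 × (1 - exp(-6λ)) = 5.006; doubled, 10.01, or 99.1% of true

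| Half-life (h) | Literal AUC0-24 / true | AUC0-infinity / interval AUC | Share of AUC0-infinity beyond 6 h | 2 × AUC0-12 / true | Share of AUC0-12 beyond 6 h |
|---|---|---|---|---|---|
| 2.5 | 52% | 1.05 | 26% | 99.0% | 22% |
| 3.5 | 56% | 1.14 | 38% | 99.1% | 29% |
| 5 | 62% | 1.30 | 51% | 99.4% | 35% |
| 7 | 68% | 1.54 | 61% | 99.7% | 40% |

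**Wider assumptions** (ka 1.0 and 2.0/h, half-life 2-8 h, two-point slope): literal AUC0-24 is 51-73% of true, and AUC0-infinity is 1.02-1.77 times the interval AUC. With a three-point slope these become 52-89% and up to 3.4 times. Twice AUC0-12 stays at 99-106% under either slope.

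**New/old comparison.** Old ka 1.2/h, equal true exposure, half-life 2.5-7 h, same literal method on both days:

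| New ka (/h) | AUC0-24 ratio (truth 1.00) | AUC0-infinity ratio | AUC0-12 ratio, log-linear extrapolation |
|---|---|---|---|
| 2.0 | 0.97-0.99 | 0.94-0.99 | 1.00 |
| 0.8 | 1.05-1.08 | 1.05-1.17 | 1.01-1.02 |
| 0.6 | 1.12-1.19 | 1.14-1.44 | 1.03-1.04 |

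With equal absorption the ratio is 1.00.

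**The pre-dose value as the 12-hour value.** With a log trapezoid from 6 to 12 h this gives 98-99% of the true interval AUC when the previous dose was exactly 12 h earlier. If that one gap was 14-16 h, it gives 84-93%. Log-linear extrapolation gives 89-97% for the same gaps.

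**The switch.** If the old-formulation day is read as a real 24 hours, the new-formulation dose supplies 31-49% of the AUC (ka 1.0 and 2.0/h, half-life 2-8 h, second dose at 6 or 12 h). It supplies none of the 0-6 h data. On the new-formulation day, residual old drug is 0-14% of AUC0-12 on Day 2 and below 0.1% on Day 5.

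**The case against.** A reader might infer that the plan's exposures are wrong. The documents do not support that: they report no exposure values, only parameters to be derived. Nor does any section say that one dose will be extrapolated to 24 h with the second ignored. The words "will be determined as appropriate using standard noncompartmental procedures (WINNONLIN software" leave room for twice AUC0-12, which performs well. This stands, and it makes the 52-68% a consequence of the literal reading only. It does not remove the point: the synopsis lists AUC0-24 without that qualifier, and no rule steers the analyst to the better reading.

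A reader might also infer that the switch contaminates the old-formulation profile. It does not. The new product is taken after the last sample, and a steady-state 24-hour estimate can still be made from the morning interval.

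The within-formulation error also overstates the risk to the comparison. Subjects, times and method are the same on both days, so much of it cancels. For new ka 0.8-2.0/h, the AUC0-24 ratio is off by only -3% to +8% and the AUC0-infinity ratio by -6% to +17%.

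Finally, the objective is secondary and the planned summaries are descriptive, with no equivalence margin or decision rule. That is right, and it sets the severity. Writing CL/F and V/F instead of Cl and Vd is a labelling matter.

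**Conclusion.** The point holds as a minor one. The two named AUCs do not match what the sampling and dosing can support. Read literally, AUC0-24 is about 52-68% of true twice-daily exposure. AUC0-infinity is about 1.05-1.54 times the interval AUC and 26-61% extrapolated. The new/old ratio is biased when absorption differs: modestly for AUC0-24 at moderate differences, up to 12-19% at new ka 0.6/h, and more for AUC0-infinity.

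The observed 0-6 h data are valid on both days. What is absent is a measured 24-hour old-formulation exposure and a rule for deriving one. All percentages depend on the assumed one-compartment model, ka, half-life and 12-hour interval. The effect is confined to a secondary PK objective in about 10 patients; EFS and the sample sizes are untouched.

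**What to change.** In the synopsis and section 12.1:

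- Replace AUC0-24 and AUC0-infinity with observed AUC0-6, Cmax and steady-state AUC over the 12-hour dosing interval.
- Fill 6-12 h by log-linear extrapolation. Use the pre-dose value as the 12-hour value only when the recorded previous dose was about 12 h earlier.
- Report any 24-hour value as twice the interval AUC, and say so.
- Base apparent clearance on the interval AUC and label it CL/F; label volume V/F.
- Record the time of the previous dose on the CRF, and report the extrapolated share for each subject and day.
- Report new-formulation results by sampling day.

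**Cost:** wording in two places and one extra CRF item; no added samples or visits.

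**Downsides:** the interval AUC assumes steady state, which may not hold on Day 2, when only one new-formulation dose has been taken. With log-linear filling, 22-40% of it is still extrapolated in the model above. A long gap before the sampled dose lowers either version, so recording the gap exposes the error without correcting it.
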